4.2.1.1 Supportive of primary analyses

Supportive analyses will be performed for the primary variable. The FAS will be used unless otherwise specified. All supportive analyses are summarized below and in Table 4-1.

- 1) To assess the impact of study drug discontinuation to the results observed, a supplementary analysis using the same negative binomial model as in the primary analysis will be performed on relapses on study drug (i.e., relapses will be counted only up to study drug discontinuation) in the FAS. The number of days on study drug is calculated as (the last core dose date – 1st core dose date +1).
- 2) A supplementary analysis using the same negative binomial model as in the primary analysis will be performed on all relapses (i.e., confirmed and unconfirmed relapses) in the FAS.
- 3) Analyses on confirmed relapse and on all relapse will be repeated on the PPS.

Table 4-1 Primary efficacy endpoint, primary & supportive/sensitivity analyses

Endpoint	Analysis method	
ARR (confirmed relapses only) (time-based)	Negative binomial model (treatment, region, pubertal status (the stratification factor in IVRS), and number of relapses within the previous two years before randomization) on FAS	Primary analysis
	Negative binomial model (treatment, region, pubertal status (the stratification factor in IVRS), and number of relapses within the previous two years before randomization) excluding data after drug discontinuation on FAS	Supportive analysis
	Negative binomial model (treatment, region, pubertal status (the stratification factor in IVRS), and number of relapses within the previous two years before randomization) on PPS	
ARR (confirmed and unconfirmed relapses) (time-based)	Negative binomial model (treatment, region, pubertal status (the stratification factor in IVRS), and number of relapses within the previous two years before randomization) on FAS	Supportive analysis
	Negative binomial model (treatment, region, pubertal status (the stratification factor in IVRS), and number of relapses within the previous two years before randomization) on PPS	
ARR (confirmed relapses only) (time-based)	Negative binomial model (treatment, region, pubertal status (the stratification factor in IVRS), and number of relapses within the	Sensitivity analysis

	previous two year before randomization) on FAS but exclude patients in the IFN-beta arm who are neutralizing-antibody (Nabs) positive at end of study visit	
--	---	--

In addition, ARR (time-based) and ARR (subject-based) will be calculated and summarized by treatment group. Summaries will be provided for ARR counting confirmed relapses only and for ARR counting both confirmed and unconfirmed relapses.

4.2.1.2 Handling dropouts/censorings in ARR calculations

The primary NB model with an offset for the time in study adjusts for various treatment duration and missing information (drop-out or censoring at the time of study completion) under the assumption of non-informative drop-out, information missing at random, and constant relapse rate over time. According to the protocol, subjects who discontinue study treatment should remain in the study and follow the assessment schedule. All subjects in the FAS will be included in the primary analysis, i.e., the number of confirmed relapses observed up to the end of subject’s participation in the study. Relapses will be counted regardless of whether a subject is on or off study drug.

4.2.1.3 Sensitivity analysis

To assess the impact of patients positive for NAbs on the primary efficacy outcome (i.e., confirmed relapse), the negative binomial model will be rerun on the FAS population but exclude patients in the IFN-beta arm who are Nabs-positive at the end of study visit (Table 4-1).

4.2.2 Secondary analyses

Secondary efficacy variables will be analyzed on the FAS except for the key secondary efficacy variable, annualized rate of the number of new/newly enlarged T2 lesions, which will be analyzed additionally on the PPS as supportive analyses as well as on the FAS population but exclude patients in the IFN-beta arm who are Nabs-positive at the end of study visit as a sensitivity analysis.

Secondary analyses (including both the key secondary analysis and other secondary analyses) are summarized in Table 4-2 and Table 4-4 (for MRI analysis in section 4.2.2.4) and details will be provided in the following sections. The FAS will be used unless otherwise specified. P-values for the treatment comparisons will be provided. Each inferential analysis will be performed at a significance level of 0.05 with no adjustment for multiple analyses.

Table 4-2 Key and Other secondary efficacy variables & analyses

Endpoint	Analysis method	
Key secondary		
Annualized rate of the number of new/newly	Negative binomial regression (treatment, region, pubertal status (the stratification factor in IVRS), and baseline T2 lesions), offset: time in	Key secondary analysis

enlarged T2 lesions up to Month 24	study on FAS	
	Negative binomial regression (treatment, region, pubertal status (the stratification factor in IVRS), and baseline T2 lesions), offset: time in study on PPS	Supportive analysis
	Negative binomial model (treatment, region, pubertal status (the stratification factor in IVRS), and baseline T2 lesions), offset: time in study on FAS but exclude patients in the IFN-beta arm who are Nabs-positive at end of study visit	Sensitivity analysis
Other Secondary		
Time to first confirmed relapse and proportion of patients free of relapse	Log-rank test stratified by treatment group	Supportive analysis
	Cox's proportional hazard model (treatment, region, pubertal status (the stratification factor in IVRS), and number of relapses within the previous two years before randomization)	Supportive analysis
Number of T1 Gd-enhancing lesions per scan up to Month 24	Negative binomial regression (treatment, region, pubertal status and baseline T1 Gd-enhancing lesions), offset: number of scans. The response variable is the cumulative number of T1 Gd-enhancing lesions from each visit up to Month 24	Supportive analysis

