5.3 Treatment assignment

Core Phase:

At Visit 3, all eligible patients will be randomized via Interactive Voice Response (IVR) system to one of the two treatment arms. The investigator or his/her delegate will contact the IVR system after confirming that the patient fulfills all the inclusion/exclusion criteria. The IVR system will assign a randomization number to the patient, which will be used to link the patient to a treatment arm and will specify a unique medication number for the first package of study drug to be dispensed to the patient. The randomization number will not be communicated to the caller.

Fingolimod Extension Phase:

At Visit 15 (first Extension Phase visit), all eligible patients will be assigned via Interactive Voice Response (IVR) system to receive either 0.25 mg/d or 0.5 mg/d fingolimod.

Patients randomized in the Core Phase to receive fingolimod will continue to receive the same dose of fingolimod that they were receiving at Visit 14 / EOS-CP (End of Core Phase treatment) Note: A dose increase at Visit 15 is possible if the patient had a sustained increase in weight to >40 kg at two consecutive visits at least three months apart.

Patients randomized to receive interferon- β -1a during the Core Phase of the study will be assigned to receive fingolimod (0.5 or 0.25 mg/d based on body weight as described in [Section 5.1](#). Note: The body weight of a patient must be sustained at >40 kg at two consecutive visits at least three months apart for a patient to receive the 0.5 mg/d dose of fingolimod at the start of the Extension Phase.

The randomization numbers for the Core Phase will be generated using the following procedure to ensure that treatment assignment is unbiased. A patient randomization list will be produced by the IVR system provider using a validated system that automates the random assignment of patient numbers to randomization numbers. These randomization numbers are linked to the different treatment arms, which in turn are linked to medication numbers. A separate medication list will be produced by or under the responsibility of Novartis Drug Supply Management using a validated system that automates the random assignment of medication numbers to study drug packs containing each of the study drugs.

Randomization will be stratified by region, due to the anticipated low number of patients that will be enrolled at each site, and by puberty status (pre-pubertal and pubertal).

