9.5.2 Efficacy variables

Core Phase:

Secondary and exploratory efficacy variables will be summarized by visit. Descriptive statistics (mean, standard deviation, median, minimum and maximum) will be provided for variables that are of the numeric or continuous type, while frequency distributions (with number and percent) will be provided for variables that of the categorical type.

P-values for the treatment comparisons will be provided. Each inferential analysis will be performed at a significance level of 0.05 with no adjustment for multiple analyses.

Secondary and [REDACTED] efficacy variables that are of the continuous or numeric type (such as the number of Gd-enhanced T1 lesions per scan, [REDACTED] will be analyzed via a negative binomial regression model adjusted for treatment, pubertal status, region, and relevant baseline value.

The volume of Gd-enhanced T1 lesions, change from baseline in T2 hyperintense and [REDACTED] lesion volume on MRI and percent brain volume change from baseline will be analyzed via a rank ANCOVA model adjusted for treatment, pubertal status, region and relevant baseline values. The percent brain volume change from baseline will also analyzed via an ANCOVA model with similar factor and covariates.

Time to event variables (such as the time to first confirmed relapse up to end of study-Core Phase) will be analyzed using the log-rank test (for comparing event-time distributions). In addition, a Cox regression model adjusted for treatment, number of relapses in the previous two year before study enrollment, pubertal status, and region will also be performed. Estimates of the hazard ratio and its 95% confidence intervals, and the p-value for treatment comparison from the Cox model will be provided. The Kaplan-Meier estimates of time to event variables and the relapse-free proportions at Month 24 will also be provided.

Fingolimod Extension Phase:

To examine long-term efficacy of continuous fingolimod treatment vs interferon β -1a switch to fingolimod treatment, the following endpoints will be analyzed by Core Phase treatment assignment and combined based on Fingolimod Treated FAS if not otherwise specified.

The efficacy variables will be summarized by visit or yearly intervals for the patients with continuous fingolimod treatment and the patients switched from IFN β -1a to fingolimod treatment. Descriptive statistics (mean, standard deviation, median, minimum and maximum)

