3.8.7 Last dose day of randomized study medication

The last dose date of the randomized study drug will be collected on three eCRFs:

- 1) The last date patient took study drug on the study phase completion eCRF,
- 2) The study drug discontinuation date on the study drug discontinuation eCRF, and
- 3) The last end date on the study drug administration record eCRF.

The last dose date recorded in the study phase completion eCRF (included in the CMP data panel with visit number 778) will be used.

4 Efficacy evaluation

Unless otherwise specified, all efficacy analyses will be based on the Full Analysis Set, following the intention-to-treat principle. Analysis of the primary efficacy variable will also be conducted on the per-protocol set, as well as the analyses on the key secondary variable. Treatment group estimates will be determined using least-squares means estimates.

All statistical models will be adjusted by the two randomization stratification factors: region and pubertal status reported in IVRS based on investigator's assessment. Pooling of regions with small patient count will be performed for better model fitting based on patient count in the region and geographic proximity. As a result, there will be three regions: East Europe, West Europe, rest of the regions (pooled by three small regions with <20 patients for each: Australia, Middle and South America, and North America). A stratification factor may also be considered to be removed from the model in presence of extremely small stratum with scarce information or given model converge problem.

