4.2.2.3.1 Time to first relapse and proportion of relapse-free subjects

Time to first relapse and proportion of relapse-free subjects are considered as other secondary endpoints related to relapses.

For subjects with at least one event (i.e., relapse), time to event is calculated as (event start date – 1st core dose date + 1). For subjects without event, time to event will be calculated the same as the time in study for ARR in [Section 4.1.2](#).

The log-rank test of the treatment difference in the Kaplan–Meier estimates of the survival function of the time to first relapse will be performed.

Kaplan-Meier (KM) estimates of the survival functions will be constructed by treatment group. KM estimates of the relapse free patients at 12 and 24 months, together with 95% confidence intervals will be presented. Two-sided 95% confidence intervals of the difference in KM estimates will also be presented. The corresponding KM plot will be provided.

Cox’s proportional hazards model adjusted for treatment, region, pubertal status (the stratification factor in IVRS), and number of relapse within the previous two year before randomization will be performed as a supportive analysis. Estimates of the hazard ratio and its 95% confidence intervals, and the p-value for treatment comparison from the Cox model will be provided.

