4.2.2.3.2 Relapse characteristics

The following relapse characteristics will be summarized at relapse level: severity (mild/moderate/severe), affecting daily activities (yes/no), steroid used (yes/no), hospitalization (yes/no), recovery status (none/partial/complete), and duration of relapse (days).

The following relapse characteristics will be summarized at patient level: severity, affecting daily activities, steroid used, hospitalization, and recovery status. For summaries at patient level, a patient is counted only in the most severe category for each variable.

Summaries of the above mentioned relapse characteristics will be performed for confirmed relapses and for all relapses (confirmed and unconfirmed) as well.

The proportion of subjects hospitalized for relapse and the proportion of subjects with severe relapses will be compared between treatment groups using a Chi-square test.

The severity of confirmed MS relapses will be derived according to the criteria in [Table 4-3](#). For severity derivation, the EDSS data obtained on the date of relapse confirmation (as collected on the Relapse eCRF page) will be used.

Table 4-3 Severity of MS relapse

Mild relapse	Moderate relapse	Severe relapse
EDSS increase of 0.5 point	EDSS increase of 1 or 2 points	Exceeding Moderate criteria
Or	Or	Or
1 point FS change in one to three systems	2-point FS change in one or two systems	Exceeding Moderate criteria
	Or	Or
	1-point change in four or more systems	Exceeding Moderate criteria

[Panitch et al 2002]

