10.1.1.5 Survival analysis for time to event variables

Log-rank test will be used to compare the survival distributions of two treatment groups for secondary efficacy time to event variables, for example time to first confirmed relapse. The analyses were performed on the full analysis set.

The log-rank test statistic compares estimates of the hazard functions of the two groups at each observed event time. It is constructed by computing the observed and expected number of events in one of the groups at each observed event time and then adding these to obtain an overall summary across all time points where there is an event.

Cox proportional hazards model is to estimate the effect parameter(s) without any consideration of the hazard function assuming the proportional hazards assumption holds. The proportional hazards assumption is the assumption that effect parameters multiply hazard: for example, if taking drug X halves your hazard at time 0, it also halves your hazard at time 1, or time 0.5, or time t for any value of t. The effect parameter(s) estimated by any proportional hazards model can be reported as hazard ratios. Below is an example of the SAS codes to perform the Log-rank test with Kaplan-Meier Method and the Cox proportional hazards model.

```
*****
* SAS Codes: LOG-RANK test with Kaplan-Meier Method
* Variables in the model:
* reltm = time to first confirmed relapse
* trt = treatment group code
* relcens = censor flag (1=censored, 0=not censored)
*****.
proc lifetest data=eff method=km;
  where trt in ('A', 'B');
  time reltm*relcens(1);
  strata trt;
run;
*****
* SAS Codes: Cox's regression model
* Variables in the model:
* reltm = time to first confirmed relapse
* trt = treatment group code
```

```

* reg1a = region code
* n2 = number of relapses within the previous 2 years before randomization
* bledss = baseline EDSS
* relcens = censor flag (1=censored, 0=not censored)
*****;
proc phreg data=datain nosummary;
  class trt reg1a/ order=internal parm=GLM;
  model reltm*relcens(1)=trt n2 bledss reg1a/rl ties=exact;
  contrast "A vs B" trt 1 -1/estimate=exp;

ods output parameterestimates=pest;
ods output contrastestimate=est;
run;

```

**Note that data set pest contains Hazard ratio estimates from model statement. If parameter='trt', then SELECT probchisq hazardratio hrlowercl hruppercl for results;

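### The log-rank test for time to first relapse is mislabelled and unstratified, and the Cox example code omits pubertal status, so as coded neither analysis uses both randomization strata

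*SAP*

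**What the plan says.** **Strata and general rule.** Protocol 5.3 states "Randomization will be stratified by region" and, in the same sentence, by puberty status. The opening of SAP section 4 sets the rule for analysis: "All statistical models will be adjusted by the two randomization stratification factors: region and pubertal status reported in IVRS". It pools regions to three and lets a factor be dropped if a stratum is extremely small or a model fails to converge.

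**Log-rank test.** Time to first confirmed relapse is an other secondary endpoint (Protocol 2.2, SAP 4.2.2.3.1). Its log-rank test appears in four places:
- Protocol 9.5.2 says time-to-event variables "will be analyzed using the log-rank test (for comparing event-time distributions"). It names no strata.
- SAP 4.2.2.3.1 says "The log-rank test of the treatment difference in the Kaplan–Meier estimates of the survival function of the time to first relapse will be performed". It names no strata either.
- SAP Table 4-2 says "Log-rank test stratified by treatment group" and labels the test supportive.
- SAP 10.1.1.5 gives PROC LIFETEST code whose time statement begins "time reltm*relcens(1" and whose only STRATA variable is `trt`.

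**Cox model.** Protocol 9.5.2, SAP 4.2.2.3.1 and the next row of Table 4-2 all adjust for treatment, region, pubertal status and relapses in the previous two years, and a treatment p-value is reported. The PROC PHREG example in SAP 10.1.1.5 lists `trt`, `n2`, `bledss` and `reg1a`. That is treatment, prior relapses, baseline EDSS and region, with no term for pubertal status.

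**The concern.** There are three separate problems.

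1. **The label is wrong.** A test stratified by treatment would compare nothing within each stratum.
2. **The log-rank test leaves out the factors used to randomize.** When strata are prognostic and allocation is balanced within them, an unstratified log-rank test overstates the variance of the treatment comparison. Its p-value is then too large on average.
3. **The Cox example code does not match the Cox text.** Anyone programming from the example would leave out one randomization factor and add a covariate that the text never mentions.

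At stake are the p-values for a named secondary endpoint, each read at 0.05, and the clarity of what was prespecified. Type I error for the primary and key secondary tests is not at stake.

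**Working it through.** **1. The plan's own figure.** The documents give no event count or power for the log-rank test. The figures they do give are for the primary endpoint (SAP 9.1, Protocol Appendix 5): annual rates 0.18 and 0.36, T = 2 years, κ = 0.82, n = 95 per arm, two-sided 5%.
- Information = n / [1/(λ1T) + 1/(λ2T) + 2κ] = 95 / [1/0.36 + 1/0.72 + 1.64] = 95 / 5.807 = 16.36, as stated.
- Power = Φ(ln 2 × √16.36 − 1.96) = Φ(0.844) = 80.06%, against a stated 80%.

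**2. What these inputs imply for time to first relapse over 24 months.**
- P(at least one relapse) = 1 − (1 + κμ)^(−1/κ). This is 0.271 for μ = 0.36 and 0.432 for μ = 0.72.
- Expected events = 95 × (0.271 + 0.432) ≈ 67.
- Approximate marginal hazard ratio = ln(1 − 0.271) / ln(1 − 0.432) ≈ 0.56.
- Schoenfeld power = Φ(√67/2 × |ln 0.557| − 1.96) ≈ 67%.

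**3. What the code does.** In PROC LIFETEST, a STRATA statement without the GROUP= option names the groups to be compared. So `strata trt;` gives a valid two-group log-rank test with no stratification. The literal reading of Table 4-2 and the code are therefore different tests.

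**4. Coverage of the two strata.**

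| Analysis | Region | Pubertal status |
|---|---|---|
| Log-rank, text and Table 4-2 | not named | not named |
| Log-rank, code | no | no |
| Cox, text and Table 4-2 | yes | yes |
| Cox, code | yes | no (baseline EDSS added) |

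**5. Size of the effect.** Two simulations compared the unstratified test with one stratified by region and puberty, each with 190 patients and 4,000 runs. All stratum shares and effects are assumptions.

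*Simulation A:* regions 45/35/20%, 8% pre-pubertal, hazard ratio 0.5, uniform censoring between 0.3 and 2 years.

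| Region effect | Power, unstratified | Power, stratified |
|---|---|---|
| none | 80.8% | 79.7% |
| HR 2 | 77.8% | 78.1% |
| HR 3 | 75.8% | 77.7% |

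Size under the null at region HR 3 was 4.1% unstratified and 5.2% stratified.

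*Simulation B:* regions 45/40/15%, 8% pre-pubertal, blocks of 4 within six strata, gamma frailty with κ = 0.82, two years' follow-up, rate ratio 0.5. The stratum ratio applies to each region step and also to puberty.

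| Stratum ratio | Size, unstratified | Size, stratified | Power, unstratified | Power, stratified |
|---|---|---|---|---|
| 1 | 4.7% | 4.6% | 67% | 66% |
| 1.5 | 5.0% | 5.3% | 63% | 64% |
| 2 | 4.0% | 4.9% | 61% | 63% |
| 3 | 3.3% | 5.2% | 53% | 59% |

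The last row is extreme. A ratio of 3 per step is 3 × 3 = 9-fold across three regions, with a further factor of 3 for puberty. The Monte Carlo standard error of a 5% size is √(0.05 × 0.95 / 4000) ≈ 0.3 points, so differences of a few tenths of a point should not be read closely.

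**The case against.** The strongest reply is that this is an editorial slip with little consequence. Much of that stands.

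- **The endpoint as a whole.** A reader might infer that time to first relapse is tested without the randomization strata. The documents do not support this: the Cox model, in the text of both documents, adjusts for both factors and reports a treatment p-value. The gap is in the log-rank test and in the Cox example code.
- **The wrong test being run.** A reader might infer from Table 4-2 that the analysis cannot compare treatments. SAP 4.2.2.3.1 asks for a test of the treatment difference, and the code delivers a valid one. The table cell probably echoes SAS syntax.
- **A broken rule or a departure from the protocol.** Protocol 9.5.2 also names no strata, so the SAP does not depart from it. The rule in SAP section 4 speaks of models, so whether it reaches a log-rank test is arguable, and it allows a very small stratum to be dropped. However, the SAP does not invoke that exception here or give any reason for leaving the strata out.
- **Example code.** The SAP presents its code as examples, so the text may be meant to govern. That softens the Cox mismatch but does not remove it.
- **Importance.** The endpoint is outside the test hierarchy, no power is claimed for it, and Table 4-2 labels both analyses supportive.
- **The Chi-square tests.** Severe and hospitalized relapses "will be compared between treatment groups using a Chi-square test", also without strata. No calculation was made for these, and they are not part of this point.

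**Conclusion.** The point holds in a limited form. Table 4-2 mislabels the log-rank test, the test is coded unstratified after stratified randomization, and the Cox example code contradicts its own text. As coded, neither time-to-event analysis uses both strata.

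The statistical cost is small. A reader might fear a false-positive problem, but the unstratified test showed no inflation in any scenario: its size was between 3.3% and 5.0%. The effect on power runs from an advantage of about 1 point for the unstratified test with no stratum effect, to a loss of about 2 points at region HR 3, to about 6 points under the extreme region and puberty effects. These figures depend on assumed stratum shares and effects, because the documents say nothing about how prognostic region or puberty is. The case for changing the text rests mainly on correct and consistent specification, with any gain in power second.

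**What to change.** - **Table 4-2 and SAP 4.2.2.3.1:** replace the description with: log-rank test of treatment, stratified by pooled region and IVRS pubertal status.
- **Log-rank code in SAP 10.1.1.5:** replace `strata trt;` with `strata reg1a pub / group=trt;`, where `reg1a` holds the three pooled regions and `pub` is the IVRS pubertal status, named as in the negative binomial example.
- **Cox code in SAP 10.1.1.5:** add pubertal status to the CLASS and MODEL statements and remove baseline EDSS, so that it matches 4.2.2.3.1 and Protocol 9.5.2.

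The cost is a few lines of text and code, plus about 1 point of power if the strata turn out not to be prognostic. A stratum with patients from only one arm contributes nothing to the stratified test, which is a negligible loss.

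Replacing the two Chi-square tests in SAP 4.2.2.3.2 with Cochran-Mantel-Haenszel tests on the same strata would be consistent with this change but is optional.
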